#### **Safety Analyses:**

The Safety Analysis Set (SAF) is defined as all subjects who receive at least 1 dose of study treatment (ASP1128 or placebo).

The safety evaluation will be based mainly on AEs, clinical laboratory and vital signs. Descriptive statistics will be used to summarize safety data. All safety data will be summarized by treatment.

All summaries of AEs will include only treatment-emergent events unless otherwise stated. AEs will be categorized by system organ class and preferred term using MedDRA.

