6. Safety central laboratory tests including serum creatinine (SCr) and cystatin C.
7. If the subject is discharged from hospital after day 7, the last result of SCr before discharge from local laboratory testing will be collected.
8. UO assessment: from T0 (visit 2) to T72 (visit 5) when the subject is in the ICU, UO will be recorded every 12 hours and fluid intake will be recorded every 24 hours. The eCRF should indicate when UO data have to be recorded from the subject ICU record. During the first 72 hours following surgery (i.e., visits 3 to 5), the investigator will be asked to record information on AKI-UO stages 1 to 3 in the eCRF to assess their occurrence as per investigator discretion. When the subject is discharged from the ICU, but is still in the hospital UO and fluid intake every 24 hours will be recorded up to day 7 (visit 8).
9. Include albuminuria dipstick.
10. The first dose of investigational product (IP)/study drug to be administered as soon as possible after the NC AKIRisk score is assessed between 2 and 22 hours after T0 is  $> 0.3$  (ng/mL)/1000 to allow completion of first treatment within 24 hours after T0. If the first dose of IP administration is completed within 8 hours after T0, the second dose of IP will be administered at 24 hours after T0 and the third dose of IP will be administered at 48 hours after T0. If the first dose of IP administration is completed past 8 hours after T0, the second dose of IP will be administered at 16 hours after the start of the first dose, and the third dose of IP will be administered at 40 hours after the start of the first dose of IP.  
Second and third dosing of the IP: a 2-hour treatment window before or after designated administration time is allowed.
11. Additional urine samples will be taken and stored to assess various clinical and compound related biomarkers.
12. AE will be collected from informed consent until visit 9 or until the subject is determined to be a screen failure. If the subject is discontinued from the study prior to visit 9, AEs will be collected until the EoS visit has been completed. After the end of all the procedures of visit 9 until visit 10, only serious AEs will be collected.
13. Assess data on renal replacement therapy, mortality, ICU stay, total hospital stay and duration of mechanical ventilation (time ventilation weaning, i.e., time from T0 to extubation).

*Footnotes continued on next page*

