## **5.5 Adverse Events and Other Safety Aspects**

### **5.5.1 Definition of Adverse Events**

An AE is any untoward medical occurrence in a subject administered a study drug, which does not necessarily have to have a causal relationship with this treatment. An AE can therefore be any unfavorable and unintended sign (including an abnormal laboratory finding), symptom, or disease (new or exacerbated) temporally associated with the use of a medicinal product whether or not considered related to the medicinal product.

In order to identify any events that may be associated with study procedures and could lead to a change in the conduct of the study, Astellas collects AEs even if the subject has not received study drug treatment. AE collection begins after the signing of the ICF.

For screen failures, AEs will be collected until the subject is determined to be a screen failure.

For randomized subjects, all AEs will be collected until visit 9. If the subject is discontinued from the study prior to visit 9, AEs will be collected until the EoS visit has been completed. After end of all the procedures of visit 9 until visit 10, only SAEs will be collected.

For subjects in the observational cohort, AEs will be collected until 24 hours after T0. However, AEs related to MAKE parameters will be collected until the EoS visit. This includes events resulting in death or in RRT or relating to reduction in renal function.

Care will be taken not to introduce bias when detecting AEs and/or SAEs. Open-ended and non-leading verbal questioning of the subject is the preferred method to inquire about AE occurrences.

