## 6.2 Safety Variables

Safety will be assessed by evaluation of the following variables:

- Treatment-emergent adverse events (TEAEs; frequency, severity, seriousness, and relationship to study drug).

- Clinical laboratory variables (hematology, biochemistry including liver enzymes and total bilirubin, and urinalysis)
- Vital signs (systolic and diastolic blood pressure and pulse rate)

TEAE is defined as an AE observed after starting administration of the study drug and by visit 9 (day 30). If the adverse event occurs on Day 1 and the onset check box is marked “Onset after first study drug taken” or the onset check box is left blank, then the adverse event will be considered treatment emergent. If the adverse event occurs on Day 1 and the onset check box is marked “Onset before first study drug taken”, then the adverse event will not be considered treatment emergent. If a subject experiences an event both during the pre-investigational period and during the investigational period, the event will be considered as TEAE only if it has worsened in severity (i.e., it is reported with a new start date).

A study drug-related TEAE is defined as any TEAE with a causal relationship of YES by the investigator or with missing assessment of the causal relationship.

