### **7.5.1 Adverse Events**

Summaries and listings of serious adverse events (SAEs) and Serious TEAEs include SAEs upgraded by the sponsor based on review of the Sponsor's list of Always Serious terms if any upgrade was done.

The coding dictionary for this study will be MedDRA. It will be used to summarize AEs by system organ class (SOC) and preferred term (PT).

An overview table will include the following details:

- Number of TEAEs,
- Number and percentage of subjects with TEAEs,
- Number of drug related TEAEs,

- Number and percentage of subjects with drug related TEAEs,
- Number of serious TEAEs,
- Number and percentage of subjects with serious TEAEs,
- Number of serious drug related TEAEs,
- Number and percentage of subjects with serious drug related TEAEs,
- Number of TEAEs leading to death,
- Number and percentage of subjects with TEAEs leading to death,
- Number of TEAEs leading to withdrawal of treatment,
- Number and percentage of subjects with TEAEs leading to withdrawal of treatment,
- Number of drug related TEAEs leading to withdrawal of treatment,
- Number and percentage of subjects with drug related TEAEs leading to withdrawal of treatment, and
- Number of deaths.

The number and percentage of subjects with TEAEs, as classified by SOC and PT will be summarized for each treatment group. Summaries will be provided for:

- TEAEs
- Drug related TEAEs,
- serious TEAEs,
- Drug related serious TEAEs,
- TEAEs leading to death,
- Drug related TEAEs leading to death,
- TEAEs leading to withdrawal of treatment,
- Drug related TEAEs leading to withdrawal of treatment,
- TEAEs excluding serious adverse events that equal to or exceed a threshold of 5.0% in any treatment group,
- Frequently reported TEAEs that equal to or exceed a threshold of 5.0% in any treatment group, and
- Frequently reported drug related TEAEs that equal to or exceed a threshold of 5.0% in any treatment group.

The number and percentage of participants with TEAEs, as classified by PT only, will be summarized for each treatment group.

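### SAEs are collected to Day 90, but the SAP tabulates them by arm only to Visit 9; apart from deaths and the Day-90 renal and hospital endpoints, later ones are only listed

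*Protocol*

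**What the plan says.** **Collection.** For randomized subjects, Protocol Table 1 (footnote 12) has all AEs collected until Visit 9 and then narrows to serious ones: "After the end of all the procedures of visit 9 until visit 10, only serious AEs will be collected". Protocol 5.5.1 repeats the rule: "After end of all the procedures of visit 9 until visit 10, only SAEs will be collected". Collection starts well before dosing: "AE collection begins after the signing of the ICF".

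**Definition.** SAP 6.2 sets the window: "TEAE is defined as an AE observed after starting administration of the study drug and by visit 9 (day 30"). Protocol 7.5.1 uses the same definition.

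**Tabulation.** The protocol synopsis gives the default under Safety Analyses: "All summaries of AEs will include only treatment-emergent events unless otherwise stated". SAP 7.5.1 follows it. The overview has a row "Number and percentage of subjects with serious TEAEs", and the SOC/PT tables for serious, drug-related serious and fatal events are all TEAE tables. The table by time interval ends at Day 30. One overview row carries no treatment-emergent label: "Number of deaths". Protocol 7.5.1 sends all AEs to a listing.

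**A loose end.** SAP 7.5.1 opens with a sentence that names SAE summaries apart from serious-TEAE summaries: "Summaries and listings of serious adverse events (SAEs) and Serious TEAEs include SAEs upgraded by the sponsor". No SAE table outside the treatment-emergent window is then specified.

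**The concern.** Safety and tolerability is a secondary objective (Protocol 2.1.2), and the safety endpoint is the nature, frequency and severity of AEs (Protocol 2.3.4). Sites report SAEs through Visit 10, and the investigator judges causality for each one (Protocol 5.5.3). If those reports are only listed, a difference between arms in the kind of late serious event, for example stroke, infection or arrhythmia, would have to be found by reading individual records. A late SAE judged related to study drug would enter no drug-related table. A fatal event that starts after Visit 9 would not appear among TEAEs leading to death, so its cause would not be tabulated by arm.

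**Working it through.** The plan gives no figure of its own here. The check has two parts: how long the uncovered stretch is, and what the plan still compares within it.

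**Length of the stretch.** Inputs from Protocol Table 1: Visit 9 at Day 30 (window Day 23 to 37), Visit 10 at Day 90 (window Day 83 to 97), screening at the earliest on Day -28.

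Share of the postsurgery period after Visit 9 = (Visit 10 day - Visit 9 day) / Visit 10 day.

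- Nominal days: (90 - 30)/90 = 60/90 = 66.7%.
- Latest Visit 9, earliest Visit 10: (83 - 37)/83 = 46/83 = 55.4%.
- Earliest Visit 9, latest Visit 10: (97 - 23)/97 = 74/97 = 76.3%.

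Counted from the earliest possible consent, the denominator grows by 28 days:

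- Nominal: 60/(90 + 28) = 60/118 = 50.8%.
- Across the windows: 46/111 = 41.4% to 74/125 = 59.2%.

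The postsurgery denominator suits a comparison between arms, because randomization and dosing come after surgery. It is not the whole SAE collection period.

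**What is compared by arm after Visit 9.**

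| Information | By-arm analysis in the SAP | What is missing |
|---|---|---|
| Death | Overview row of deaths (7.5.1, no cut-off stated); Day-90 mortality (7.4.4); MAKE90 (7.4.2) | Cause, if the fatal event began after Visit 9 |
| RRT, eGFR loss of 25% or more | Day-90 endpoints (7.4.4); MAKE90 (7.4.2) | Causality, grade |
| Hospital and ICU days, readmissions | Wilcoxon tests (7.4.4) | Event type, causality, grade |
| Non-fatal SAE by SOC/PT | None | Listing only |
| Drug-related SAE | None | Listing only |
| SAE by CTCAE grade | None | Listing only |
| SAE by time interval | Ends at Day 30 (7.5.1) | Visit 9 to Visit 10 |

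The first three rows are analyzed on the FAS and the AE tables on the SAF. Both sets require at least one dose, so the choice of set matters little. The gap lies in the lower rows: event type, causality and grade of late SAEs.

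**The case against.** **Late serious outcomes are compared.** A reader might infer that nothing serious after Visit 9 is compared between arms. The documents do not support that. Deaths, RRT, eGFR loss and MAKE90 are compared by arm, and so are hospital and ICU days to Day 90 and readmissions. Inpatient hospitalization is itself an SAE criterion (Protocol 5.5.2), so an excess of hospitalized late events could show in readmissions. This stands and narrows the point. It does not close the gap, because three different events that each cause a readmission look the same in those analyses.

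**The Visit 9 cut is reasonable.** The two documents agree on it. The third dose falls at most 24 + 40 + 2 = 66 hours after T0. The longest half-life range reported in phase 1 ends at 17.4 hours, so five half-lives add 87 hours: 66 + 87 = 153 hours, about 6.4 days. A TEAE window to about Day 30 is ample, and this stands. It is a reason to keep the TEAE tables, not a reason to leave later SAEs untabulated after collecting them.

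**The table may exist elsewhere.** The opening sentence of SAP 7.5.1 speaks of SAE summaries, and SAP 7.1 refers to separate TLF specifications that are not available here. What can be said is that SAP 7.5.1 specifies no such table, while the stated default is treatment-emergent events only.

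**The moving Visit 9.** Because Visit 9 may fall anywhere from Day 23 to Day 37, a reader might want treatment emergence closed on a fixed day. That would not work cleanly: non-serious AE collection stops at the actual Visit 9, so a subject seen on Day 23 would have days counted as treatment-emergent with no non-serious AEs collected. The same window applies to both blinded arms, and nothing in the documents shows a bias from it.

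**Conclusion.** The point holds in a limited form. SAEs starting between Visit 9 and Visit 10 are collected in both arms, but SAP 7.5.1 specifies no by-arm table of them by event type, causality or grade, and no table of cause for deaths from events that begin in that period. The stretch is nominally 60 of 90 postsurgery days (67%), or 55% to 76% across the visit windows.

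Two stronger readings should be resisted. One is that two thirds of the SAE collection period goes uncovered: collection starts at consent, and from Day -28 the nominal share is about 51%. The other is that two thirds of SAEs go untabulated: a share of days is not a share of events. The documents give no SAE rate from which a count could be worked out.

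The conclusion rests on the tables that the SAP names and assumes that the TLF specifications add none of this kind. The protocol and SAP do not contradict each other here, and neither alpha nor power is affected. This is a free improvement.

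**What to change.** Leave the TEAE definition and all TEAE tables as they are. In SAP 7.5.1:

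1. Add a by-arm SOC/PT table on the SAF of all SAEs from first dose to Visit 10/EoS, with Visit 9 to Visit 10 shown as a separate interval. This also supplies the SAE summary that the section's opening sentence implies.
2. Add a by-arm table of deaths to Visit 10 with cause.
3. State the cut-off for the overview row that counts deaths.

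The cost is one or two extra tables and a line of wording. The data are already collected, so there is no added burden on subjects or sites.

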**Table 2 Schedule of Assessments – Subjects in the Observational Cohort**

| Study Period                       | Screening         | Surgery        |                   |                 | Follow-up Period |                 |                 |                |                 |                      | Unscheduled    |
|------------------------------------|-------------------|----------------|-------------------|-----------------|------------------|-----------------|-----------------|----------------|-----------------|----------------------|----------------|
|                                    |                   | Visit Number   | 1                 | 2   | 3                | 4               | 5               | 8              | 9  | 10/EoS  |                |
| Day                                | -28               | pre            | peri  | post            | 2                | 3               | 4               | 7/DoD          | 30              | 90                   |                |
| Visit Window                       | ≥ -28 days        | -              | -                 | -               | T0 + 24 hours    | T0 + 48 hours   | T0 + 72 hours   | 4 to 7 days    | 23 to 37 days   | 83 to 97 days        |                |
| Assessment                         |                   |                |                   |                 |                  |                 |                 |                |                 |                      |                |
| Informed Consent                   | X                 |                |                   |                 |                  |                 |                 |                |                 |                      |                |
| Inclusion/exclusion criteria       | X                 |                |                   |                 |                  |                 |                 |                |                 |                      |                |
| Medical history, demographics      | X                 |                |                   |                 |                  |                 |                 |                |                 |                      |                |
| Medication use                     | X                 | X              | X                 | X               | X    |                 |                 |                |                 |                      |                |
| Physical examination               | X    |                |                   |                 |                  |                 |                 |                |                 |                      |                |
| Body weight, height                | X                 |                |                   |                 |                  |                 |                 |                |                 |                      |                |
| Subject randomization              |                   |                |                   |                 |                  |                 |                 |                |                 |                      |                |
| Vital signs                        | X                 | X              |                   |                 |                  |                 |                 |                |                 |                      |                |
| Hematology, biochemistry           | X  | X  |                   |                 | X    | X   | X   | X  | X   | X        |                |
| Urinary output        |                   |                |                   | X               | X                | X               | X               | X              |                 |                      | O              |
| Urinalysis                         | X  | X  |                   |                 |                  |                 |                 | X  | X   | X        | X  |
| Pregnancy test                     | X  | X  |                   |                 |                  |                 |                 |                |                 |                      |                |
| NephroCheck®                       |                   |                |                   | X  | X   | X  | X  |                |                 |                      |                |
| Biomarkers             |                   | X              |                   | X               | X   | X  | X  |                |                 |                      |                |
| Assessment of AEs                  | X                 | X              | X                 | X               | X    |                 |                 |                |                 |                      |                |
| Assess follow-up parameters        |                   |                |                   |                 |                  |                 |                 |                |                 |                      |                |
| Assess MAKE parameters             |                   |                |                   |                 | X                | X               | X               | X              | X               | X                    |                |
| APACHE-II              |                   | X              |                   | X               |                  |                 |                 |                |                 |                      |                |
| EQ-5D-5L                           |                   | X              |                   |                 |                  |                 |                 |                |                 |                      |                |
| Blood samples for pharmacokinetics |                   |                |                   |                 |                  |                 |                 |                |                 |                      |                |
| Blood samples for pharmacodynamics |                   |                |                   |                 |                  |                 |                 |                |                 |                      |                |
| Biobanking sample PGx              |                   | X              |                   |                 |                  |                 |                 |                |                 |                      |                |

*Footnotes appear on next page*

AE: adverse event; APACHE-II: acute physiology and chronic health evaluation II; DoD: day of discharge from hospital; EoS: end of study; EQ-5D-5L: 5-level European Quality of Life 5 Dimensions Questionnaire; MAKE: major adverse kidney events; O: if possible; PGx: pharmacogenomics; T0: time point 0; UO: urine output.

1. The preoperative period is defined as the part of the day of surgery before the incision. The peri-operative period is defined as the period between incision and T0 (i.e., the time point when the subject comes off the cardiopulmonary bypass pump [CPB]). The postoperative period is the period after T0.
2. During surgery, the following data have to be assessed in the electronic case report form (eCRF): Procedures (coronary artery bypass graft surgery and/or valve surgery, thoracic aortic surgery, extracorporeal membrane oxygenation, use of ventricular assist device, redo cardiac surgery) and duration of CPB; lowest intraoperative mean arterial pressure; perioperative fluid balance and medication (fluid intake, UO, blood products, drain output, blood loss, inotropics/vasopressors and furosemide); time of incision and closing of skin; T0 and perioperative complications.
3. Central laboratory tests
4. Additional urine samples will be taken and stored to assess various clinical and compound related biomarkers.
5. APACHE-II score is recorded on visit 2 preoperatively, postoperatively. Results from local laboratory testing can be used, and the result closest to the indicated time points should be recorded.
6. Visit 1 can be close to the day of surgery. If the results from the central laboratory testing of AST, ALT, total bilirubin and eGFR are not yet available at time of randomization, results from local laboratory can be used for verifying randomization requirements if assessed within 7 days before the day of surgery up to initiation of surgery. When the surgery is scheduled within 2 days after screening visit 1 and it is not feasible to perform blood and/or urine samplings at visit 1, the sampling at visit 1 can be by-passed if the results from local laboratory are available for verifying randomization requirements.
7. Presurgery pregnancy test at the day of surgery will be assessed locally with urine dipstick test.
8. AEs and medication use will be collected until 24 hours after T0. However, AEs related to MAKE parameters will be collected until the EoS visit. AEs will be followed up until resolved including medication use for the AE.
9. Local laboratory test results will be collected from medical records, including serum creatinine and serum cystatin C (if available).
10. 24-hour urinary output data will be collected from medical records (if available).
11. Subjects will only be randomized if postoperative NephroCheck® (NC) AKIRisk® score (assessed between 2 to 22 hours after T0) is  $> 0.3 \text{ (ng/mL)}^2/1000$ . If the AKIRisk score is  $\leq 0.3 \text{ (ng/mL)}^2/1000$ , the subject cannot be randomized and will be followed up in the observational arm.
12. Urine sampling only for NC and biomarker assessments if subjects are still in the intensive care unit and urine can be sampled from the catheter. Urine samples will be taken, but frozen until later assessment at the central laboratory.
13. Visit 9 and 10 may be conducted by phone if the subject is unable to visit the site and will require contact for MAKE parameters collection.
14. When an assessment of a full physical examination is available and performed within 30 days before surgery, the assessment can be used even if it was performed prior to the informed consent.

